### 7.1.1.1 Information to be Collected on Clinical Screening Failures

Subjects who sign the ICF but do not start study treatment for any reason will be considered Clinical Screening failures. The following eCRF pages must be completed for all Clinical Screening failures:

- Clinical Screening Disposition page (including reason for the subject not starting study treatment).
- Informed consent.
- Demography.
- Adverse events (only if an SAE occurs).
- Inclusion/exclusion criteria.

### 7.1.2 Treatment Phase

The Treatment Phase begins on Cycle 1 Day 1 with the first administration of avelumab and will continue until progression (see Sections 6.2 and 7.3.3), significant clinical deterioration (clinical progression), unacceptable toxicity, or any criterion for withdrawal from the study or IMP occurs

(see Sections 5.5.1 and 5.5.2). However, a subject may remain on avelumab beyond RECIST 1.1-defined disease progression if their ECOG performance status has remained stable, there are no new symptoms or worsening of existing symptoms, and, if in the opinion of the Investigator, the subject will benefit from continued treatment with avelumab (see Section 6.2). For subjects who continue avelumab beyond progression, treatment should be stopped immediately if the subject no longer tolerates avelumab or if therapeutic failure occurs. See Section 6.2.

[figure not shown]
Re-initiation of avelumab may be allowed in a subject who discontinues administration of avelumab but subsequently fails to confirm and verify original PD and meets the Criteria for Continuation of Treatment Beyond Progression (See Section 6.2 and 7.3.3).

Subjects receiving avelumab who have experienced a CR should be treated for a minimum of 12 months, and/or until disease progression or unacceptable toxicity, after confirmation of response.

For subjects receiving avelumab once every 2 weeks, subjects will be asked to visit the study site every 2 weeks during the Treatment Phase. A time window of up to 3 days before or 1 day after the scheduled visit day (- 3/+ 1 days) will be permitted for all study procedures (except PK sampling visits on Days 2 and 3).

For subjects receiving avelumab once weekly, subjects will be asked to visit the study site once weekly for the first 12 weeks, and then once every 2 weeks starting at Week 13 during the Treatment Phase. A time window of 1 day before or 1 day after the scheduled visit day (- 1/+ 1 days) is permitted for all study procedures while subjects receiving avelumab once weekly (12 consecutive weeks). A time window of up to 3 days before or 1 day after the scheduled visit day (- 3/+ 1 days) will be permitted for all study procedures while subjects receiving avelumab once every 2 weeks (Week 13 and thereafter).

CCI

The assessments to be performed during the Treatment Phase are detailed in Table 1-1 for subjects receiving avelumab once every 2 weeks; in Table 1-2 for subjects receiving avelumab once a week for the first 12 weeks followed by once every 2 weeks (10 mg/kg once weekly cohort).

### **7.1.3 End-of-Treatment Visit**

Subjects must undergo an EOT Visit after discontinuation of avelumab for any reason. The EOT Visit should be performed within 7 days after the decision to discontinue treatment, but before any new anticancer therapy is started (if possible), whichever occurs earlier. The EOT Visit may be performed on the day of the decision to discontinue avelumab.

Any subject who experiences an AE that mandates discontinuation of avelumab should have an EOT Visit as soon as possible after the decision to discontinue avelumab (within 7 days).

The EOT Visit eCRF page should be completed with a visit date reflecting the date the discontinuation decision was made, with the last known date the subject received avelumab, and 1 of the following reasons:

- Adverse event(s).
- Abnormal laboratory value(s).
- Abnormal test procedure result(s).
- Protocol violation.
- Subject withdrew consent.
- Lost to follow-up.
- Death (must state if death is due to “Study Indication” or “Other” reason).

CCI

- Treatment duration completed as per protocol (for subjects who experience a confirmed CR; see Section 6.2).
- Other reasons, including clinical deteriorations, administrative problems.

CCI

Please refer to [Table 1-1](#), [Table 1-3](#), [Table 1-4](#), and [Table 1-5](#) for the specific assessments to be performed at the EOT Visit.

## 7.1.4 Safety Follow-up

The safety parameters to be assessed during the Safety Follow-up (30-day Safety Follow-up Visit and 90-day Phone Call) are detailed in [Table 1-1](#), [Table 1-3](#), and [Table 1-4](#).

### 7.1.4.1 30-day Safety Follow-up Visit

All subjects will have a Safety Follow-up Visit scheduled 30 days ( $\pm 5$  days) after the last administration of avelumab.

After the EOT Visit, all AEs have to be documented until the 30-day Safety Follow-up Visit. After this visit, all SAEs and all treatment-related nonserious AEs must be documented until the 90-day Safety Follow-up Phone Call. Subjects with an ongoing SAE at the 30-day Safety Follow-up Visit

must be monitored and followed up by the Investigator until stabilization or until the outcome is known.

#### **7.1.4.2 90-Day Phone Call**

At 90 days ( $\pm 5$  days) after the last dose of avelumab, subjects will be contacted by telephone to collect information on new or ongoing SAEs and treatment-related nonserious AEs. Any SAE assessed as related to study treatment must be reported whenever it occurs, irrespective of the time elapsed since the last administration of avelumab. Subjects will also be asked about any anticancer therapy.

#### **7.1.5 Long-term Follow-up**

Subjects with an SAE ongoing after the Safety Follow-up Phone Call must be monitored and followed-up by the Investigator until stabilization or until the outcome is known, unless the subject is documented as “lost to follow-up”.

After the EOT Visit, subjects will be followed every 12 weeks ( $\pm 7$  days) for survival (including the assessment of any further anticancer therapy). Survival follow-up will continue until 2 years after the last subject receives the last dose of avelumab, or the last subject dies, whichever occurs first. Additional survival follow-up data may be collected at the time of primary and final analyses if the last follow-up data were collected more than 30 days earlier. Under some circumstances, subjects may not be followed for survival for 2 years in this study, eg, subjects may be given the opportunity to participate in a rollover study, or the Sponsor may terminate the study early.

Each subject will be followed for survival until death, lost to follow-up, or the cutoff date of the End of Study (Section 5.7).

The assessments to be performed at the Long-term Follow-up Visits are detailed in [Table 1-1](#).

### **7.2 Demographic and Other Baseline Characteristics**

The assessments and procedures described in this section must be performed during Clinical Screening.

#### **7.2.1 Demographic Data**

At screening, the following data will be collected:

- Date of birth
- Sex
- Race
- Ethnicity.

## 7.2.2 Diagnosis of Tumor

The tumor disease information to be documented and verified at the Clinical Screening Visit for each subject includes:

- Detailed history of the tumor including histopathological diagnosis, grading and staging in accordance with the International Union Against Cancer Tumor Node Metastasis Classification of malignant tumors at diagnosis.
- All therapy used for prior treatment of the tumor (including surgery, radiotherapy, chemotherapy, and immunotherapy).
- Any other conditions that were treated with chemotherapy, radiation therapy, or immunotherapy.
- Current cancer signs and symptoms, and AEs effects from current and/or previous anticancer treatments.
- Current cancer disease status.

## 7.2.3 Medical History

In order to determine the subject's eligibility to participate in the study, a complete medical history will be collected and documented during Clinical Screening. This will include, but may not be limited to, the following:

- Past and concomitant nonmalignant diseases and treatments.
- Past and concomitant malignant diseases and treatments.
- All medications (including herbal medications) taken and procedures carried out within 30 days prior to screening.
- Smoking and alcohol history.
- Family cancer history.

[figure not shown]
## 7.2.4 Other Baseline Assessments

All other baseline measurements, such as tumor evaluation, vital signs, complete physical examination, ECOG performance status (see Section 12, Appendix IV), clinical laboratory parameters, 12-lead ECG, and biomarker will be assessed as detailed in Table 1-1 and Table 1-2.

[figure not shown]
Please refer to Sections 7.3.1 and 7.3.2 for details of baseline tumor evaluations, Section 7.4 for baseline safety evaluations, CCI [REDACTED].

For study entry, all subjects must fulfill all the inclusion criteria described in Section 5.3.1 and not meet any of the exclusion criterion described in Section 5.3.2.

CCI

CCI

[figure not shown]
CONFIDENTIAL  
INFORMATION

79/137

Document No. CCI [REDACTED]

Object No. CCI [REDACTED]

CCI

## 7.4 Safety Assessments

The safety profile of avelumab will be assessed through the recording, reporting, and analyzing of baseline medical conditions, AEs, physical examination findings, vital signs, and laboratory tests.

Comprehensive assessment of any apparent toxicity experienced by the subject will be performed throughout the course of the study, from the time of the subject's signature of informed consent. Study site personnel will report any AE, whether observed by the Investigator or reported by the

CONFIDENTIAL  
INFORMATION

80/137

Document No. CCI [REDACTED]

Object No. CCI [REDACTED]

subject (see Section 7.4.1.2). Given the intended mechanism of action of avelumab, particular attention will be given to AEs that may follow the enhanced T cell activation such as dermatitis, colitis, hepatitis, uveitis, or other immune-related reactions. Ophthalmologic examinations should be considered, when clinically indicated, for signs or symptoms of uveitis.

The reporting period for AEs is described in Section 7.4.1.3. The safety assessments will be performed according to Table 1-1 and Table 1-2.

## **7.4.1 Adverse Events**

### **7.4.1.1 Adverse Event Definitions**

#### **Adverse Event**

An AE is any untoward medical occurrence in a subject or clinical investigation subject administered a pharmaceutical product, which does not necessarily have a causal relationship with this treatment. An AE can therefore be any unfavorable and unintended sign (including an abnormal laboratory finding), symptom, or disease temporally associated with the use of a medicinal product, whether or not considered related to the medicinal product.

In cases of surgical or diagnostic procedures, the condition/illness leading to such a procedure is considered as the AE rather than the procedure itself.

The Investigator is required to grade the severity/intensity of each AE.

Investigators will reference the NCI-CTCAE v4.03 (publication date: 14 June 2010). This is a descriptive terminology that can be used for AE reporting.

A general grading (severity/intensity) scale is provided at the beginning of the referenced document, and specific event grades are also provided.

If the severity/intensity of a particular AE is not specifically graded by the guidance document, the Investigator is to revert to the general definitions of Grade 1 through Grade 5 and use his or her best medical judgment.

The 5 general grades are:

- Grade 1: Mild
- Grade 2: Moderate
- Grade 3: Severe
- Grade 4: Life-threatening or disabling
- Grade 5: Death.

According to the Sponsor's convention, if a severity/intensity of Grade 4 or Grade 5 is applied to an AE, then the Investigator must also report the event as an SAE. However, a laboratory abnormality with a severity/intensity of Grade 4, such as anemia or neutropenia, is considered serious only if the condition meets one of the serious criteria described below.

In the case of death, the primary cause of death (the event leading to death) should be recorded and reported as an SAE. "Fatal" will be recorded as the outcome of this respective event; death will not be recorded as separate event. Only if no cause of death can be reported (eg, sudden death, unexplained death), the death per se might be reported as an SAE.

Investigators must also systematically assess the causal relationship of AEs to the study treatment using the following definitions. Decisive factors for the assessment of causal relationship of an AE to avelumab include, but may not be limited to, temporal relationship between the AE and avelumab, known side effects of avelumab, medical history, concomitant medication, course of the underlying disease, study procedures.

**Not related:** Not suspected to be reasonably related to the study treatment. The AE could not medically (pharmacologically/clinically) be attributed to the treatment under study in this protocol. A reasonable alternative explanation must be available.

**Related:** Suspected to be reasonably related to the study treatment. The AE could medically (pharmacologically/clinically) be attributed to the IMP under study in this protocol.

### **Abnormal Laboratory Findings and Other Abnormal Investigational Findings**

Abnormal laboratory findings and other abnormal investigational findings (eg, on an ECG trace) should not be reported as AEs unless they are associated with clinical signs and symptoms, lead to treatment discontinuation or are considered otherwise medically important by the Investigator. If an abnormality fulfils these criteria, the identified medical condition (eg, anemia, increased ALT) must be reported as the AE rather than the abnormal value itself.

### **Adverse Drug Reaction**

An ADR is defined in this study as any AE suspected to be related to avelumab by the Investigator and/or Sponsor.

### **Serious Adverse Event**

An SAE is any untoward medical occurrence that at any dose:

- Results in death.
- Is life-threatening.

**Note:** The term "life-threatening" in this definition refers to an event in which the subject is at risk of death at the time of the event; it does not refer to an event that hypothetically might cause death if it were more severe.

- Requires inpatient hospitalization or prolongation of existing hospitalization.
- Results in persistent or significant disability/incapacity.
- Is a congenital anomaly/birth defect.
- Is otherwise considered as medically important.

Important medical events that may not result in death, be life-threatening, or require hospitalization may be considered as SAEs when, based upon appropriate medical judgment, they may jeopardize the subject or may require medical or surgical intervention to prevent 1 of the outcomes listed in this definition. Examples of such events include allergic bronchospasm requiring intensive treatment in an emergency room or at home, blood dyscrasias or convulsions that do not result in inpatient hospitalization, or the development of drug dependency or drug abuse.

For the purposes of reporting, any suspected transmission of an infectious agent via an IMP is also considered a serious adverse reaction and all such cases should be reported in an expedited manner as described in Section 7.4.1.4.

#### **Events that Do Not Meet the Definition of a Serious Adverse Event**

Elective hospitalizations to administer, or to simplify study treatment or study procedures (eg, an overnight stay to facilitate chemotherapy and related hydration therapy application) are not considered as SAEs. However, all events leading to unplanned hospitalizations or unplanned prolongation of an elective hospitalization (eg, undesirable effects of any administered treatment) must be documented and reported as SAEs.

#### **Events Not to Be Considered as Adverse Events or Serious Adverse Events**

Medical conditions present at the initial study visit that do not worsen in severity or frequency during the study are defined as baseline medical conditions and are NOT to be considered AEs.

#### **Adverse Events/Serious Adverse Events Observed in Association with Disease Progression**

Progression of the disease/disorder being studied assessed by measurement of lesions on radiographs or other methods as well as associated clinical signs or symptoms (including laboratory abnormalities) should not be reported as an (S)AE, unless the patient's general condition is more severe than expected for the participant's condition and/or unless the outcome is fatal within the adverse event reporting period (as defined in Section 7.4.1.3).

#### **Predefined AEs of Special Interest for Safety Monitoring**

Any AE that is suspected to be a potential irAE and infusion-related reactions will be considered an adverse event of special interest.

### Dose-limiting Toxicity

A DLT is defined as a  $\geq$  Grade 3 ADR according to the NCI-CTCAE v4.03, occurring during the DLT observation period of the dose escalation cohorts. An ADR is defined in this study as any AE suspected to be related to avelumab by the Investigator and/or Sponsor. A DLT must be confirmed by the SMC as being related to avelumab.

A DLT is specifically defined as any Grade  $\geq$  3 toxicity that is possibly, probably, or definitely related to avelumab, occurring during the DLT observation period, except for any of the following:

- Grade 3 infusion-related reaction resolving within 6 hours and controlled with medical management.
- Transient ( $\leq$  6 hours) Grade 3 flu-like symptoms or fever, which is controlled with medical management.
- Transient ( $\leq$  24 hours) Grade 3 fatigue, local reactions, headache, nausea, emesis that resolves to  $\leq$  Grade 1.
- Grade 3 skin toxicity, or Grade 3 LFT (ALT, AST, or gamma-glutamyl transferase) increase that resolves to  $\leq$  Grade 1 in less than 7 days after medical management (eg, immunosuppressant treatment) has been initiated.
- Grade 3 diarrhea unless to be discontinued according to Treatment Guidelines. In this case it would be an DLT again.
- Single laboratory values out of normal range that are unlikely to be related to avelumab according to the Investigator, do not have any clinical correlate, and resolve to  $\leq$  Grade 1 within 7 days with adequate medical management.
- Tumor flare phenomenon defined as local pain, irritation, or rash localized at sites of known or suspected tumor.

The ADRs (including DLTs) that require permanent discontinuation of avelumab are described in Section 5.1.3.1.

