In 10 mg/kg once weekly cohort, the SMC will evaluate overall safety data when all 6 evaluable subjects have completed a minimum 4-week treatment period, and after 12 weeks of observation has been completed for all subjects enrolled in this cohort (see Section 2.1).

See Section 5.1.2.1.2 and Figure 5-3 for further details of the dose escalation algorithm, and Section 5.2.2 for a discussion of the rationale for dose selection.

Subjects will not be replaced unless the subject does not fulfill the requirement for dose determination. Dose determination is achieved when the subject receives 2 doses of avelumab at the scheduled regimen and completes the minimal 21-day safety observation period (DLT observation period) unless they discontinue due to a DLT. For the definition of a DLT, see Section 7.4.1.1.

The design of the dose escalation is based on Studies EMR100070-001 and EMR100070-002 and therefore allows for the ethnic sensitivity of avelumab to be evaluated across studies.

The overall study design is shown in Figure 5-1.

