### 5.1.3.1 Adverse Drug Reactions Requiring Treatment Discontinuation or Modifications

The following adverse drug reactions (ADRs) require permanent discontinuation or treatment modification of avelumab treatment:

- Any Grade 4 ADRs: permanently discontinue avelumab except for laboratory values out of normal range that do not have any clinical correlation.
- Any Grade 3 ADRs:
  - Withhold avelumab except for laboratory values out of normal range that do not have any clinical correlate.
  - Permanently discontinue avelumab if toxicity does not resolve to Grade  $\leq 1$  or baseline within 12 weeks of last administration or if the same Grade 3 toxicity recurs (consider consult with the medical monitor before permanently discontinuing the treatment).
- Infusion should not be given if ECOG performance status is  $\geq 3$  on the day of study treatment administration. Treatment should be discontinued if ECOG performance status has not improved to  $\leq 2$  by the next scheduled treatment administration.
- Any Grade 2 ADRs should be managed as follows:
  - Infusion should not be given in case of ongoing Grade 2 ADR on the day of study treatment administration.
  - Treatment can be resumed according to original schedule\* once ADR resolved to Grade  $\leq 1$ . Up to 2 subsequent study drug doses may be omitted. If more than 2 doses are skipped, treatment may be resumed after consultation with the Medical Monitor.

\*Original schedule is defined as “the dosing schedule calculated according to first dose”.

If dosing is delayed more than 4 weeks, treatment may be resumed after consultation with the study Medical Monitor. Any delay in dosing in excess of 12 weeks is not permitted.

Infusion-related reactions and irAEs should be handled according to the guidelines provided in Sections 6.5.5.1 and 6.5.5.2, respectively.

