**Table 6-1 Management of Hypersensitivity and Infusion-related Reactions Caused by Avelumab**

NCI-CTCAE Grade	Treatment Modification for Avelumab
Grade 1: Mild Mild transient reaction; infusion interruption not indicated; intervention not indicated	
 
Decrease avelumab infusion rate by 50% and monitor closely for any worsening.
 

Grade 2: Moderate Therapy or infusion interruption indicated but responds promptly to symptomatic treatment (eg, antihistamines, nonsteroidal antiinflammatory drug, narcotics, intravenous fluids); prophylactic medications indicated for ≤ 24 hours	
 
Temporarily discontinue avelumab infusion
 
Resume infusion at 50% of previous rate once infusion-related reaction has resolved or decreased to at least Grade 1 in severity and monitor closely for any worsening.
 

Grade 3 or Grade 4: Severe or Life-threatening Grade 3: Prolonged (eg, not rapidly responsive to symptomatic medication and/or brief interruption of infusion); recurrence of symptoms following initial improvement; hospitalization indicated for clinical sequelae Grade 4: Life-threatening consequences; urgent intervention indicated	
 
Stop the avelumab infusion immediately and disconnect infusion tubing from the subject
 
Subjects have to be withdrawn immediately from avelumab treatment and must not receive any further avelumab treatment.
 

NCI-CTCAE: National Cancer Institute-Common Terminology Criteria for Adverse Events.

Once the avelumab infusion rate has been decreased by 50% or interrupted due to an infusion-related reaction, it must remain decreased for the next scheduled infusion. If no infusion-related reaction is observed in the next scheduled infusion the infusion rate may be returned to baseline at the all subsequent infusions. If an infusion reaction occurs, all details about drug preparation and infusion must be recorded.

Subjects should be instructed to report any delayed reactions to the Investigator immediately.

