## 8.4 Analysis Sets

- **Screening Analysis Set:** all subjects who signed the ICF(s).
- **DLT Analysis Set:** all subjects with data used for implementing the dose-escalation schedule (excluding 6 subjects in 10 mg/kg once weekly cohort). These subjects should have received all avelumab administrations in the DLT observation period (first 21 days of treatment) or should have stopped treatment because of DLTs in the DLT observation period.
- **Safety Analysis Set:** all subjects who have received at least 1 dose of avelumab. The Safety Analysis Set will be used for all analyses of safety and efficacy.
- **Efficacy Population:** all subjects who have received at least 1 dose of avelumab and have measurable disease at baseline according to Investigator assessment.
- **PK Analysis Set:** all subjects who have completed at least 1 infusion of avelumab, and who have provided valid PK samples.

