### 8.5.2 Analysis of Primary Endpoints

#### 8.5.2.1 DLTs in Dose Escalation Cohorts

DLT is defined in Section 7.4.1.1. The number and proportion of subjects experiencing DLTs will be reported by dose level based on the DLT Analysis Set (excluding 10 mg/kg once weekly cohort).

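### A short Grade 3 infusion reaction at the first infusion is not a DLT but ends treatment, so neither the event nor the subject appears in the primary DLT table

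*Protocol*

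**What the plan says.** The primary safety result is defined in Protocol 8.5.2.1: "The number and proportion of subjects experiencing DLTs will be reported by dose level based on the DLT Analysis Set". SAP 15.1 repeats it. Five provisions decide who and what enters that proportion.

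- **DLT definition (Protocol 7.4.1.1).** A related Grade 3 or higher toxicity in the 21-day window is a DLT, with exceptions. One exception is a "Grade 3 infusion-related reaction resolving within 6 hours and controlled with medical management".
- **Management (Protocol Table 6-1).** For Grade 3 or 4 infusion reactions: "Subjects have to be withdrawn immediately from avelumab treatment and must not receive any further avelumab treatment". There is no exception for short duration. Protocol 5.1.3.1 makes this table the governing rule: "Infusion-related reactions and irAEs should be handled according to the guidelines provided in Sections 6.5.5.1 and 6.5.5.2, respectively".
- **DLT Analysis Set (Protocol 8.4, same wording in SAP 8.2).** Subjects "should have received all avelumab administrations in the DLT observation period (first 21 days of treatment) or should have stopped treatment because of DLTs".
- **Evaluability (Protocol 5.1.1.1).** "Dose determination is achieved when the subject receives 2 doses of avelumab at the scheduled regimen", together with 21 days of observation. The only excuse is discontinuation due to a DLT.
- **Replacement (Protocol 5.1.1.1).** "Subjects will not be replaced unless the subject does not fulfill the requirement for dose determination".

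**The concern.** The exemption and the withdrawal rule were written for different purposes and meet badly in the analysis set. A subject who stops at the first infusion because of a related Grade 3 reaction has not received both doses and has not stopped for a DLT. The documents do not say how such a subject is classified, so by default the subject is not evaluable and can be replaced.

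The same list of exemptions shows that the difficulty was recognised elsewhere. Grade 3 diarrhea becomes a DLT again if the treatment guidelines require discontinuation. The infusion-reaction exemption has no such clause. Nor has the exemption for short Grade 3 liver-test rises, although Protocol Table 6-2 permanently discontinues avelumab for Grade 3 ALT or AST rises managed as hepatic immune-related events.

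With cohorts of 3 to 6 and a threshold of 2 DLTs, one or two subjects matter. Infusion reactions are the first identified risk listed in Protocol 3.4. A reader of the DLT table would see a full cohort of six and could not tell that a further treated subject had stopped for related Grade 3 toxicity.

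**Working it through.** **The plan's own figure.** Lower total: 3 (3 mg/kg) + 6 (10 mg/kg every 2 weeks) + 6 (20 mg/kg, filled for PK) + 6 (10 mg/kg weekly) = 21. Upper total: 6 + 6 + 6 + 6 = 24. Both match the synopsis. Neither contains an allowance for replacements.

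**The path of one subject** with a related Grade 3 reaction at the first infusion that resolves within 6 hours:

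| Question | Rule | Answer |
|---|---|---|
| Is it a DLT? | Protocol 7.4.1.1 | No, exempt |
| May treatment continue? | Table 6-1 via 5.1.3.1 | No, permanently withdrawn |
| All doses in 21 days? | Days 1 and 15 | No, Day 15 missed |
| Stopped because of a DLT? | Protocol 8.4, SAP 8.2 | No |
| In the DLT set? | Protocol 8.4, SAP 8.2 | No |
| Replaceable? | Protocol 5.1.1.1 | Yes |

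The chain is certain only for the first infusion. At the second, the documents do not define whether an interrupted dose counts as received. The subject might stay in the set as a non-DLT. A liver-test rise follows the same path only if avelumab is discontinued before the Day 15 dose.

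**What the table shows (10 mg/kg every 2 weeks).**

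- Seven treated, one such withdrawal, no DLT. Plan: 0/6 = 0%. Subject kept as a non-DLT: 0/7 = 0%. DLT or treatment-ending related Grade 3 event: 1/7 = 14.3%.
- Eight treated, two such withdrawals, one DLT. Plan: 1/6 = 16.7%, and the dose passes. Kept as non-DLTs: 1/8 = 12.5%. DLT or treatment-ending related Grade 3 event: 3/8 = 37.5%.

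**Chance of at least one removal.** With no DLTs, 3 + 6 + 3 = 12 subjects are DLT-evaluated, because the last three at 20 mg/kg are enrolled for PK only. Let q be the probability per subject of a removing reaction at the first infusion (an assumption). The chance is 1 − (1 − q)^12:

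- q = 1%: 1 − 0.99^12 = 11.4%
- q = 5%: 1 − 0.95^12 = 46.0%
- q = 20%: 1 − 0.80^12 = 93.1%

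**Which provision does what.** Let p be the probability of a DLT as defined, exclusive of q. Among evaluable subjects it becomes p/(1 − q). The six-subject cohort passes with probability (1 − π)^6 + 6π(1 − π)^5. At p = 10% and q = 10% (both assumed):

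- plan, π = 0.10/0.90 = 0.111: 86.3%
- subject kept as a non-DLT, π = 0.10: 88.6%
- withdrawing reaction counted as a DLT, π = 0.20: 65.5%

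The large difference comes from the exemption. Dropping the subject moves the pass probability by about 2 points, and downward. Expected enrolment for six evaluable subjects is 6/0.90 = 6.7.

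**The case against.** **The numerator is settled by the DLT definition.** A reader might infer that leaving the analysis set is what removes the toxicity from the DLT proportion and biases it downward. The documents do not support that. The exempt event would be missing from the numerator even if the subject stayed in, and dropping a non-DLT subject slightly raises the expected proportion, p/(1 − q) against p. This objection stands. The 14.3% is therefore the share of treated subjects with a DLT or treatment-ending related Grade 3 toxicity, and not a corrected DLT rate.

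**Grade 2 reactions.** A reader might also infer that Grade 2 events hide dose-limiting toxicity, because "Infusion should not be given in case of ongoing Grade 2 ADR on the day of study treatment administration". A Day 15 dose missed this way does remove a subject from the set, since dosing resumes on the schedule set by the first dose and Day 29 lies outside the window. But Grade 2 events are below the DLT threshold on any reading. Several are also governed by other rules: Table 6-1 interrupts and resumes for Grade 2 infusion reactions, and Table 6-2 initially continues avelumab for Grade 1 to 2 rash and endocrinopathies. They should be listed, not counted as events.

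**The events are reported elsewhere.** SAP 15.2.2 and 15.2.5 tabulate discontinuations and infusion reactions by grade on the Safety Analysis Set, and SAP 10.1 gives reasons for stopping treatment. Under Protocol 2.1 the SMC reviews safety data generally. So it does not follow that escalation decisions are blind to these events. What is missing is the link between treated and DLT-evaluable subjects.

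**Frequency.** The only reaction rate in the available text is Grade 4: 3 of 1300, 0.2% (Protocol 3.4). Premedication is mandatory, and Table 6-1 describes Grade 3 reactions as prolonged or recurrent, which narrows the group that resolves within 6 hours. The true q may be low.

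**Conclusion.** The concern holds for a related Grade 3 infusion reaction at the first infusion that meets the exemption. It can also arise for an exempt Grade 3 ALT or AST rise managed as a hepatic immune-related event before Day 15. In these cases the primary DLT table carries no trace of a treatment-ending related Grade 3 toxicity, and neither document plans a display that would show the exclusion.

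The effect in one cohort can be 0/6 against 1/7. The chance that it arises at all is about 11% to 93% for q from 1% to 20%. That range rests entirely on the assumed q and on 12 DLT-evaluated subjects.

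The point is limited to the completeness of the primary safety table. It does not show that the DLT proportion as defined is biased downward, that events are lost from the study, or that the SMC cannot see them. It is worth correcting because the remedy is nearly free, but it does not invalidate the design.

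**What to change.** 1. **Reconcile.** The sponsor should reconcile the DLT exemptions (Protocol 7.4.1.1), Tables 6-1 and 6-2, the evaluability and replacement rule (Protocol 5.1.1.1) and the DLT Analysis Set (Protocol 8.4, SAP 8.2). The text should say how a subject withdrawn for an exempt related toxicity is classified, and whether an interrupted infusion counts as received. Which clinical rule applies is for the sponsor.
2. **Tabulate.** In SAP 15.1, list by dose level all treated escalation subjects excluded from the DLT set, with the reason. Show related Grade 3 or higher removals separately from Grade 2 removals.
3. **Sensitivity proportion.** Among all treated subjects of the DLT-evaluated cohorts, count as an event a DLT or a related Grade 3 or higher event that ends treatment within 21 days, at either infusion. Show separately the subjects enrolled at 20 mg/kg for PK only. Label the result descriptive and leave the primary DLT definition unchanged.
4. **SMC.** Supply the same table at each escalation review.

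The cost is one table and a possibly less favourable sensitivity figure. No extra data collection is needed.
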